
**VII.E.7 Will you attempt to recontact subjects who are lost to follow-up?**

No - followup is not required in this study

**VII.E.9 Will subjects be provided any compensation for participating in this study?**

No

**VIII. Risks**

**VIII.1 What are the risks to subjects including**  
**- emotional or psychological**  
**- financial**  
**- legal or social**  
**- physical?**

The care the patient will receive is standard practice at UIHC for thoracic or interventional cardiac surgeries and are necessary procedures regardless of this research study. Thus, no additional physical risk is involved. Patients may be under slightly elevated emotional stress knowing that they are part of a research study. There is a very low risk of loss of confidentiality of the patient's medical information, yet this is unlikely as patients will be given identification numbers at the earliest date possible and these will only be accessed by members of the research team. Only the data necessary to answer the research question will be collected upon reviewing patient information. There are no other known financial, physical or legal risks to the patient.

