**I.3** **Short Title (optional):**

**I.4** **Provide a short summary of the purpose and procedures of the study proposed in this IRB application.**

- **DO NOT include information on studies not proposed in this application.**
- **Use LAY terminology only. This must be easily understandable by IRB community members and nonscientists.**
- **DO NOT cut and paste technical abstracts from funding applications that may not be understood by a general audience.**

The aim of this prospective observational study is to assess whether transesophageal echocardiography (TEE) can be used to identify the structures within the vertebral foramen of the spinal column and to determine the range of spinal segments which can be visualized. Data will be collected from both pediatric and adult patients undergoing cardiothoracic and interventional cardiac surgeries under general anesthesia. Because use of TEE is a standard surgical procedure and because TEE will already be in place to visualize the heart, no additional processes will be required to collect data, minimizing patient risk. TEE will be monitored and controlled by a trained anesthesiologist or TEE technician and visualization of the spinal cord will be confirmed. Real-time TEE images will then be captured and later graded by a trained sonographer as high, medium or low quality. Starting at the level of the tracheal bifurcation, corresponding to thoracic vertebral level T5 (Mirajalili 2012), the TEE probe will be advanced cranially to determine the spinal levels visualized above T5 and caudally in order to determine the spinal levels below T5 that can be seen on TEE. At each level seen on TEE, pictures will be taken for confirmation.

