**VI.13 Describe EACH of your subject populations**

- **Include description of any control group(s)**
- **Specify the Inclusion/Exclusion criteria for EACH group**
- **Studies under IRB-03 enrolling non veterans as part of the subject population must present a compelling argument to the IRB for the inclusion of non-Veterans (e.g., insufficient number of Veterans; survey of VA employees; study of active duty military; study involving Veterans' family members), and the research is relevant to the care of Veterans or active duty military personnel.**

The study populations will include 50 pediatric patients and 50 adult patients scheduled for cardiothoracic or interventional cardiac surgeries under general anesthesia. We will exclude any patients with known esophageal abnormalities, lesions or disease that would disqualify the patient for the use of TEE as standard procedure. We will also exclude any patients that come to the catheter laboratory exclusively for TEE exam as our study will only occur in patients already scheduled to undergo TEE use in surgery or diagnostic procedure. This will ensure that our study occurs only as a part of standard procedure and will not lengthen time under anesthesia or time in the operating room. There is no control population needed.

**VI.14 Provide an estimate of the total number of subjects that would be eligible for inclusion in each of your study populations (include your control population if applicable)**

50 pediatric patients and 50 adult patients. There is no control population needed. We expect to complete this study in one year.

**VI.15 Describe how you will have access to each of your study populations in sufficient number to meet your recruitment goals.**

Outpatient pediatric and adult cardiac surgery patients will be recruited at the cardiology clinics when patients visit for the preoperative evaluation. Inpatient cardiac patients will be identified initially by using the EPIC operating room schedule on the day before surgery. We will have access to these populations by working within the Department of Anesthesiology, and by monitoring the OR schedule for patients scheduled to undergo cardiothoracic or interventional cardiac diagnosis and surgeries. The use of TEE is standard procedure for visualizing the heart in these procedures. A trained TEE operator will be available to control and capture images. Patients will be recruited until data has been collected in 50 pediatric patients and 50 adult patients.

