**DESCRIBE:**

- **What subjects will be asked to do/what happens in the study (in sequential order)**
- **The time period over which procedures will occur**
- **The time commitment for the subject for individual visits/procedures**
- **Long-term followup and how it occurs**

The subjects of the study, scheduled to undergo cardiothoracic or interventional cardiac surgeries, will only be asked to come to their surgery. The day of surgery the patients will not be required to do anything different from standard anesthesia and surgical practice at the hospital. Subjects will come to the operating room suite and the usual monitors (electrocardiogram, non-invasive blood pressure, and oxygen saturation) will be placed. Following the routine induction of anesthesia, the Mini-Multi TEE probe (Model T6207 (21381A), Philips, Bothell, WA, USA) will be advanced to mid esophageal level in order to visualize the heart, this is standard surgical procedure in these cases. Rotation of the probe by approximately 180 degrees toward the descending aorta, with an increased gain and depth decreased to 2-3 cm, will attempt to allow for appreciation of the spinal cord and epidural space. Upon confirmation of the structures within the vertebral foramen by a trained TEE operator, an images of the spine will be captured to be later graded as high, medium or low quality by a trained sonographer. The TEE probe will then be advanced caudally and intervertebral disc spaces will be counted in order to determine the number of spinal segments that can be spanned until an image can no longer be generated. This will take approximately ten minutes, but will occur while the patient is being prepared for surgery so no additional time in the operating room will be necessary. At this point, the TEE probe will be returned to mid esophageal level to visualize the heart and the operation will proceed as usual. When looking at patient medical records, we will only collect the following data: height, weight, age, any known history of esophageal abnormalities, lesions or disease and current procedure. Ten minutes is the approximate additional time that may be required intraoperatively to observe the spinal cord on TEE but this will not extend the time in the operating room and thus no additional billing is required. No additional visits or extra time is required of the subject. There will be no necessary long-term follow up or data collection. When the patient leaves the operating room, nothing additional is required.

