**VIII.2 What have you done to minimize the risks?**

- **If applicable to this study ALSO include:**
  - **How you (members of your research team at Iowa) will monitor the safety of individual subjects.**
  - **Include a description of the availability of medical or psychological resources that subjects might require as a consequence of participating in this research and how referral will occur if necessary (e.g. availability of emergency medical care, psychological counseling, etc.)**

Healthcare professionals will monitor the subject at all times during the operation. The patient will be reassured that although they are participating in the study, everything that happens during the case is already standard practice at UIHC for thoracic and cardiac surgery patients. All patients will be given an identification number and be referred to by such. To prevent loss of confidentiality of the patient's medical information, we will keep all records used for this study in a locked office or on password protected computer system. Only members of the research team will have access to the records used in this study. No key will be kept as patients will not need to be contacted in the future.

**VIII.3 Does this study have a plan to have an individual or committee review combined data from all subjects on a periodic basis (such as summary or aggregate safety and/or efficacy data)?**

No

IX. Benefits

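### VIII.1 and VIII.2 describe the whole case as standard care, but the spinal scan in VII.E.6 is a research-only manipulation whose added risk is not known to be zero

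*Combined protocol and SAP*

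**What the plan says.** Section VIII.1 states that the care subjects receive is standard at the hospital and would be needed regardless of the research. From this it draws the conclusion "Thus, no additional physical risk is involved". Section VIII.2, on minimizing risk, says patients will be reassured that "everything that happens during the case is already standard practice at UIHC".

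Section VII.E.6 sets out the procedure. The probe is first "advanced to mid esophageal level in order to visualize the heart, this is standard surgical procedure in these cases". It is then rotated by roughly 180 degrees, with gain raised and depth cut to 2-3 cm, to look for the spinal cord and epidural space. After that, "The TEE probe will then be advanced caudally and intervertebral disc spaces will be counted", until no further image can be obtained. The probe then goes back to mid-esophageal level and the operation continues in the usual way. Section I.4 also has movement in the other direction: "the TEE probe will be advanced cranially to determine the spinal levels visualized above T5".

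On time, VII.E.6 says: "Ten minutes is the approximate additional time that may be required intraoperatively to observe the spinal cord on TEE". It adds that the scan fits within surgical preparation and does not extend operating-room time. Section VI.13 says the same of its eligibility rules: "This will ensure that our study occurs only as a part of standard procedure and will not lengthen time under anesthesia".

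**The concern.** The conclusion in VIII.1 depends on its premise that everything done to the subject is clinical care. If part of what is done is for research alone, the premise does not cover that part and the conclusion does not follow for it. The same gap makes the reassurance in VIII.2 inaccurate.

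Two things are at stake. VIII.1 is the applicant's risk statement to the IRB, which must weigh risk against the absence of direct benefit stated in IX.1. VIII.2 is something patients, or parents of minors from age 0, are to be told. There is also a smaller gap: the plan asserts that the scan costs no operating-room time, but lists no data item that would show whether this held.

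**Working it through.** No figure in the plan needs to be reproduced. The check is whether the sections agree.

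1. **What VIII.1 needs.** Its inference works only if every step that subjects undergo is standard and would happen without the study.

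2. **Sorting the steps in VII.E.6 and I.4.**
   - Usual monitors, routine induction and probe placement at mid-esophagus to view the heart: described as usual, routine or standard.
   - Rotation of about 180 degrees with changed gain and depth: done to see the spine, and not labelled standard.
   - Caudal advance with counting of disc spaces: not labelled standard. Its stopping point, loss of the spinal image, is set by the research question.
   - Cranial movement (I.4): done to find the spinal levels visible above T5.
   - Return to mid-esophagus: the operation resumes as usual.

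   The middle three steps fall outside the premise.

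3. **What other answers say about this use.** I.6 calls TEE semi-invasive and says it is not regularly used to view the spinal column. VII.B.24 answers No on FDA approval for the study use. VII.B.37 says the use is not similar to routine use. All of this fits step 2 and does not fit VIII.2.

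4. **What the ten minutes is.** VII.E.6 calls it additional, and says only that it may be required. The same section places it inside surgical preparation. It is therefore about ten minutes of probe use for research, not a stated ten minutes of extra operating-room or anesthesia time.

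5. **Who is affected.** 50 adults (VI.1) + 50 minors (VI.6) = 100 planned subjects.

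6. **Size of the added risk.** This would need a complication rate for the added manipulation, and the documents give none. I.6 and VII.B.34 cite a low complication rate for TEE in general. That supports an expectation of small added risk. It does not support zero, and no number can be computed.

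7. **What is recorded.** From the chart: "When looking at patient medical records, we will only collect the following data: height, weight, age", plus esophageal history and the current procedure. From the scan: images, later graded, and the number of segments seen. Scan duration, delay to surgery and probe-related events are not listed. VIII.3 answers No to periodic review of combined data.

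8. **What an event log could show.** With no events in n subjects, the one-sided 95% upper bound is 1 - 0.05^(1/n). For n = 50 it is 5.8%; for n = 100 it is 3.0%. These bounds describe the limit of such a log. They do not measure the defect and do not forecast harm.

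**The case against.** The strongest reply is that nothing is hidden. The same form describes the rotation, the caudal advance and the extra time, says the use lacks FDA approval, and says there is no direct benefit. It requests non-significant-risk status with reasons (VII.B.29 and VII.B.31), cites a low TEE complication rate, and promises monitoring throughout the operation (VIII.2). This stands: the fault is an inconsistency between answers, and a reader who infers concealment goes beyond the text. But these answers support a small risk, not the absence of risk claimed in VIII.1.

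Second, clinical TEE may already involve similar probe movement. The documents do not say how much, so the amount of added manipulation is unknown. Even so, the form itself calls the time additional, and the scan's purpose and stopping point belong to the research.

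Third, VII.D.29 to VII.D.36 promise that the study, its procedures and its risks will be explained. A reader might infer from VIII.2 that subjects would be misinformed overall or that consent would be defective. The documents do not support that, because the consent and assent forms cannot be seen. Only the reassurance in VIII.2 can be judged, and it is inaccurate.

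Fourth, the stated outcomes are visualization, segment range and image quality, so safety data are not strictly required. That is fair for complication counts, which could neither establish safety nor, without a control group, be attributed to the scan. Scan time and delay are different: they check a claim the plan makes. The remark in I.4 that no additional processes are needed can also stay, since it is explained there by the probe already being in place.

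**Conclusion.** The point holds as an error in two risk statements. VIII.1's conclusion does not follow for the research scan, and VIII.2's reassurance is not true of it. This affects what the IRB and all 100 planned subjects are told about a manipulation of approximately ten minutes.

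The added physical risk is unquantified. That it is small is an expectation, resting on the general TEE complication rate that the form cites and on the assumption that the scan is no more hazardous than ordinary TEE probe movement.

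A reader might also infer that the scan is unsafe or that it prolongs surgery. The documents support neither: they give no adverse rate for the scan, and VI.13 and VII.E.6 both say operating-room time is not extended. That claim is unchecked, not refuted. Multiplying ten minutes by the number of subjects would give total exposure, not risk. No estimate, sample size or analysis changes, and the visualization outcome is not biased.

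**What to change.** - **VIII.1 and VIII.2:** state that the probe is placed for clinical care, and that the spinal scan is a research-only manipulation of about ten minutes whose added physical risk is expected to be small but is not known to be zero. Remove the reassurance that the whole case is standard practice.
- **Consent and assent forms:** check that they say the same.
- **VII.E.6:** have the operator log scan start and stop time, whether surgery had to wait, and any probe-related event noticed. If events are to be taken from the patient record instead, extend the list of chart items to allow it.
- **Reporting:** describe these items by cohort, as a check on the claim of no added operating-room time and as a basic safety record. State that they are not evidence of safety and that events cannot be attributed to the scan rather than to clinical TEE.

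The cost is a slightly less favourable risk statement, rewording of three answers, a check of the forms, and a few extra data fields per case. Design, sample size and outcomes stay as they are.

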**VIII.2 What have you done to minimize the risks?**

- **If applicable to this study ALSO include:**
  - **How you (members of your research team at Iowa) will monitor the safety of individual subjects.**
  - **Include a description of the availability of medical or psychological resources that subjects might require as a consequence of participating in this research and how referral will occur if necessary (e.g. availability of emergency medical care, psychological counseling, etc.)**

Healthcare professionals will monitor the subject at all times during the operation. The patient will be reassured that although they are participating in the study, everything that happens during the case is already standard practice at UIHC for thoracic and cardiac surgery patients. All patients will be given an identification number and be referred to by such. To prevent loss of confidentiality of the patient's medical information, we will keep all records used for this study in a locked office or on password protected computer system. Only members of the research team will have access to the records used in this study. No key will be kept as patients will not need to be contacted in the future.

**VIII.3 Does this study have a plan to have an individual or committee review combined data from all subjects on a periodic basis (such as summary or aggregate safety and/or efficacy data)?**

No

IX. Benefits

**IX.1 What are the direct benefits to the subject (do not include compensation or hypothesized results)?**

There are no direct benefits to the subject.

**IX.2 What are the potential benefits to society in terms of knowledge to be gained as a result of this project?**

This novel confirmation method of visualizing the spinal cord and epidural space could be utilized in the future to detect spinal trauma, vascular events surrounding the spinal cord or detect hematoma. It could also be used in thoracic epidural catheter placement to improve the safety and success rate of epidural analgesia and potentially improve future patient care.

X. Privacy & Confidentiality

**X.1 What are you doing to protect the privacy interests of the subjects?**

To protect patient privacy, researchers will be conducting the consent and study procedures in a private setting. Further, the research team will only be collecting the information necessary to complete the study.

**X.2 Are you collecting the Social Security Number of any subjects for any purpose?**

No

**X.4 How will information/data be collected and stored for this study (check all that apply):**

- Electronic records (computer files, electronic databases, etc.) - Electronic records will be kept on the password protected Anesthesia department server. The members of the research team will be the only people with access to the files. No records will be kept on personal computers. Further, patients will be assigned a unique identification number. They will always be referred to by this number. The patient's hospital number and day of surgery will be recorded, but will not be disclosed to anyone outside the research team. We will record the hospital number only to access the patients' chart later if needed. The database that contains the identifiers will be password protected so that the only the investigators needing it can access it. No unnecessary patient identifiers will be recorded, and those that are needed will be deleted at the earliest possible time. Only data necessary to collect for the study will be recorded.
  - Name - [name]
  - Title - System Administrator and System Programmer II
  - University Job Classification - IT Security Officer
- Paper/hard copy records (hard copy surveys, questionnaires, case report forms, pictures, etc.) - Paper/hard copy records, including consent documents and any other material printed for the study, will be stored in the primary investigator's office in a locked file cabinet. Further, patients will be assigned a unique identification number. They will always be referred to by this number. The patient's hospital number and day of surgery will be recorded, but will not be disclosed to anyone outside the research team. We will record the hospital number only to access the patients' chart later if needed. The database that contains the identifiers will be password protected so that the only the investigators needing it can access it. No unnecessary patient identifiers will be recorded, and those that are needed will be deleted at the earliest possible time. Only data necessary to collect for the study will be recorded.

**X.5 Do the confidentiality protections indicated above allow only members of the research team to access the data/specimens?**

Yes

XI. Data Analysis

**XI.1 Describe the analysis methods you will use, including, if applicable, the variables you will analyze**

We are not planning to compare pediatric vs adult rates, we just want to observe the ability to image the spinal cord using TEE in this observational study. Thus, we will only use exploratory descriptive statistics for analysis.

**XI.2 Provide the rationale or power analysis to support the number of subjects proposed to complete this study.**

Because this is a novel technique, we have no base for the ability to visualize the spinal cord via TEE. We assume that fifty pediatric patients and fifty adult patients will provide adequate power to confirm that the spinal cord can adequately be observed on TEE image.

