**I.5** **Specify your research question(s), study aims or hypotheses (do not indicate "see protocol")**

The primary outcome is to identify the spinal column and epidural space on real-time TEE image, as well as to determine the range of spinal segments that can be visually spanned by TEE.

The secondary outcomes include classification of the captured TEE image as high, medium or low quality as determined by a trained sonographer.

H0: The null hypothesis is that the spinal cord and epidural space will not be visualized on real-time TEE image.

H1: The alternative hypothesis is that the spinal cord and epidural space will be successfully confirmed by real-time TEE image in all individuals.

To test this hypothesis, both pediatric and adult patients undergoing cardiothoracic or interventional cardiac surgeries under general anesthesia will be included in the study population.

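### The power claim for adequate visualization in XI.2 has no test, threshold or assumed rate behind it, and H1 in I.5 cannot be established beyond the enrolled patients

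*Combined protocol and SAP*

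**What the plan says.** Three sections bear on this point.

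- **XI.2 (sample size).** The form's prompt is "Provide the rationale or power analysis to support the number of subjects proposed to complete this study", so a rationale other than a power analysis would be acceptable. The answer first concedes that "we have no base for the ability to visualize the spinal cord via TEE" and then states: "We assume that fifty pediatric patients and fifty adult patients will provide adequate power to confirm that the spinal cord can adequately be observed".
- **XI.1 (analysis).** A pediatric-adult comparison is ruled out, and "we will only use exploratory descriptive statistics for analysis".
- **I.5 (hypotheses).** H0 reads: "The null hypothesis is that the spinal cord and epidural space will not be visualized on real-time TEE image". H1 is that "the spinal cord and epidural space will be successfully confirmed by real-time TEE image in all individuals". The section goes on: "To test this hypothesis, both pediatric and adult patients undergoing cardiothoracic or interventional cardiac surgeries" are to be included. The primary outcome also has a second part, "as well as to determine the range of spinal segments that can be visually spanned by TEE".

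VII.B.11 says that no separate written protocol will be submitted, so the documents point to no other place where a test or a calculation might be found.

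**The concern.** Power is the probability that a stated test rejects a stated null hypothesis when a stated alternative is true. XI.2 claims power, I.5 announces a test, and XI.1 plans none. The sections do not describe the same study.

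Two things are at stake. The number of patients rests on a property that the plan does not define. And the hypothesis that the study is said to test is one that a very good result would contradict: 45 of 50 patients visualized refutes H1 as worded, and the plan does not say what such a result would establish.

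**Working it through.** **1. Can the stated sample size be reproduced?** No. The inputs that a power calculation needs, and what the documents give:

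| Input | In the documents |
|---|---|
| Sample size | 50 pediatric + 50 adult = 100 (XI.2) |
| Test | None; descriptive only (XI.1) |
| Significance level, sidedness | Not stated |
| Threshold for adequate visualization | Not stated |
| Assumed rate | None; XI.2 says there is no basis for one |
| Power | No number |

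The missing inputs decide the answer. As an illustration, take an exact one-sided binomial test at 0.025 with n = 50. The level and the rates are assumptions, not figures from the plan.

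- Null rate 0.80, true rate 0.95: reject at 46 or more successes; power 90%.
- Null rate 0.80, true rate 0.90: same cut-off; power 43%.
- Null rate 0.90, true rate 0.95: reject only at 50 of 50; power 0.95^50 = 8%.

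The same 50 patients have high or negligible power depending on values that the plan does not supply.

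**2. What does H0 allow?** It has no quantifier.

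- Read as visualized in no patient (rate 0), one success refutes it. The chance of at least one success is 1 − (1 − p)^n. With n = 50 this is 1 − 0.95^50 = 92% at an assumed true rate of 5%, and 1 − 0.90^50 = 99.5% at 10%. So a technique that works in one patient in twenty would very probably refute this H0, and refuting it does not show adequacy. On this reading any count from 1 to 99 of 100 fits neither hypothesis.
- Read as not visualized in every patient, H0 and H1 are complementary, but H1 still has the difficulty in step 3.

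**3. What can be said about H1?** With all n patients visualized, the exact (Clopper-Pearson) 95% lower limit is 0.025^(1/n).

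- 50 of 50: 0.025^(1/50) = 0.929, so 92.9% to 100%. A failure rate of up to 7.1% remains compatible.
- 100 of 100: 0.025^(1/100) = 0.964, so 96.4% to 100%. A failure rate of up to 3.6% remains compatible.

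Conversely, one failure refutes H1. The chance of at least one is 1 − p^n. At an assumed true rate of 98% it is 1 − 0.98^50 = 64% in 50 patients and 1 − 0.98^100 = 87% in 100. These figures describe the wording of H1; they are not operating characteristics of a planned analysis.

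**4. What can 50 per cohort deliver?** Exact 95% intervals:

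| Result | Interval | Half of total width |
|---|---|---|
| 25/50 (widest) | 35.5% to 64.5% | 14.5 points |
| 45/50 | 78.2% to 96.7% | 9.2 points |
| 50/50 | 92.9% to 100% | 3.6 points |

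The total width is thus at most about 29 points whatever the observed rate, and this bound needs no assumed rate. Because exact intervals are asymmetric, 14.5 points is half the total width and not a limit on the distance from the estimate: at 19 of 50 (38.0%) the interval is 24.7% to 52.8%, and the upper limit lies 14.8 points away.

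No such figure can be given for the segment range. The documents plan no mean and give no standard deviation, and VII.E.6 counts disc spaces after the structures have been confirmed, so patients with failed imaging may have no count.

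**The case against.** The strongest reply is that this is openly an exploratory study. XI.1 says so, XI.2 discloses that its number is assumed and not calculated, the prompt accepts a rationale, and no test, stopping rule or decision depends on H0 or H1. All of that stands. It limits the consequence, but it does not supply the missing basis: what XI.2 offers is an assertion of power, not a feasibility or precision rationale.

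Three stronger readings are tempting, and the documents do not support them.

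- *A reader might infer that 50 + 50 is too few.* Nothing shows this. With no target there is nothing to fall short of, and for a descriptive study the precision in step 4 may well suffice.
- *A reader might infer that no power can be defined at all.* If H0 means never visualized, its rejection probability is defined and high even at low true rates (step 2). The defect is narrower: that power does not concern adequate visualization, which is what XI.2 claims to confirm.
- *A reader might infer that H1 can never be settled.* I.5 goes on directly to describe the study population, so H1 may refer to the enrolled patients only. Then 100 of 100 would settle it as an observed fact. That is not an inference and needs no power, so XI.2 gains nothing from this reading.

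**Conclusion.** The point holds in a limited form. The claim in XI.2 of power to show adequate visualization is unsupported, because the plan has no test, significance level, adequacy threshold or assumed rate, and XI.1 is descriptive only. H1 in I.5 cannot be established for the wider population by any sample; for the enrolled patients alone it would be a matter of observation; one failure refutes it either way.

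The consequence is minor to moderate. It concerns what the study can claim, not how it is run. That the inputs are missing is plain from the text. The 95% confidence level, the one-sided 0.025 and all true and null rates above are assumptions made for illustration, and the conclusion does not depend on their values.

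**What to change.** - **I.5:** replace H0 and H1, including the requirement of success in every individual, with the aim of estimating, separately in each cohort, the proportion of patients in whom the cord and epidural space are visualized. Remove the statement that a hypothesis will be tested.
- **XI.1:** report each cohort's proportion with an exact 95% confidence interval (Clopper-Pearson, for example), and describe the range of segments spanned.
- **XI.2:** replace the power sentence with the precision of 50 per cohort: total 95% interval width at most about 29 points (half the width at most 14.5 points), and a lower limit of 92.9% if all 50 are visualized. Say that the segment range has no separate sample-size target.

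As a clarification only, XI.1 could state that patients in whom imaging was attempted without success count in the denominator.

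The cost is wording in three sections and a few lines of descriptive output, with no extra patients. The downside for the investigators is a less favourable headline: an estimate with an interval in place of a statement that visualization was confirmed.
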